For the OR unfit group the ethical considerations are more difficult. The trialists are inclined to pursue a randomised trial here because we are being pressed to use EVAR in these patients. Randomisation should be between EVAR and best medical treatment against best medical treatment alone. Best medical treatment will be offered to the whole group. Smoking advice will be given and hypertension will be carefully controlled and monitored. The patients will be asked if they will be prepared to have an EVAR device in the future and if so to have CT scan or angiogram to see if their aorta would be potentially suitable for correction by an endovascular device should this be required. Patients will then be randomised to receive EVAR or not. The risks of EVAR and the potential for needing to correct by urgent open repair would be described. Undoubtedly some patients would not wish to undergo randomisation and this patient preference would be respected. Others will press for EVAR and trialists believe we should see if we can recruit patients prepared to be randomised. If trialists explain to patients that EVAR *could* be beneficial but that there is no certainty, equipoise could be achieved with some difficulty. The alternative is that some surgeons will just put them in and other centres will put in no EVAR devices. The role of a monitoring committee would be vital here as it must be possible to say to a patient that outcomes are being monitored and if EVAR looks beneficial it will be offered to that patient later. It is considered that patient preference should not formally be sought but if during the discussion before randomisation, a strong patient preference emerges this will, of course, be recognised and randomisation only applied to the equipoise patients, but no NHS funding is available for EVAR devices except as part of the randomised controlled trials, EVAR 1 & 2.

Figure 4 demonstrates the entry protocol for patients into both trials.

*Figure 4 – Summary of recruitment procedure for EVAR Trials*

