The portfolio of instruments to measure HRQL in the proposed trials is designed to be comprehensive yet brief. It will be completed by patients in the form of a questionnaire - at recruitment and subsequently one, three and 12 months after surgery or the beginning of medical treatment as appropriate. The questionnaire will include two generic instruments - the Short-Form 36-item (SF-36) Health Survey and the EuroQol. The SF-36 is a health profile comprising eight distinct scales including physical and social functioning, role limitation, mental health, vitality, pain and general health. It has been shown to be valid, reliable and responsive to changes in health in British patients. The EuroQol is a validated utility measure comprising five items covering mobility, self care, usual activities, pain, anxiety and depression. The HRQL states defined by the various combinations of responses to these items have been valued by the general public for use in cost-utility analysis. Unfortunately we know of no specific instrument designed to measure HRQL in patients suffering from AAA; this has been confirmed by a recent systematic search of Medline. One likely reason for this lack is the wide range of effects that this condition has on patients. In these circumstances we propose to use the State Trait Anxiety Inventory (STAI) which encompasses both the state form (transitory feelings of fear or worry) and the trait form (the stable tendency to respond anxiously to stressful situations or proneness). The STAI measures in-built tendency to anxious response and current feelings of anxiety. It enables the investigator to distinguish between the transitory (state) and the dispositional types of anxiety.

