#### 4.4 Economic Evaluation

Within each of the two sub-trials the type and extent of economic evaluation will depend crucially upon the clinical outcome of that trial:

1. If one technology produces a clinically better outcome than another at significantly lower cost, then clinical and financial criteria both lead to the same conclusion.
2. If there is no clinically significant difference in outcome between two technologies under comparison, then the least cost option is preferable (cost minimisation analysis).
3. If one technology produces a clinically better outcome than another at higher cost, then we shall undertake marginal cost-utility analysis (based on mortality and the EuroQol) and, if appropriate, marginal cost-effectiveness analysis (based on the Patient Generated Index (PGI)).

NHS costs will be collected. These will include the length of time in hospital (subdivided into intensive care, high dependency care, acute care and convalescent care), and theatre costs (subdivided into the length of operation and the use of staff, tests and drugs).

Under scenario 3 we shall use the EuroQol to estimate changes in health utility. One advantage of using the EuroQol is that it expresses changes in HRQL on a ratio scale. Thus cost-utility ratios in the form of cost per quality-adjusted life year (QALY) can be constructed from changes in mortality (if any) and in HRQL. Comparisons can then be made with other health care interventions. If there is no significant change in mortality, however, care will be needed because the EuroQol is less responsive to change than most condition-specific measures. To reduce the possibility of a Type II error, we shall also undertake a cost-effectiveness analysis based on the PGI.

We shall subject our results to extensive sensitivity analysis. First we shall identify the critical components of the cost and outcome by varying all estimated parameters in the analysis individually, to see how the economic findings are affected. Those parameters which lead to substantial changes in these findings will be varied over plausible ranges in combination to see whether the main conclusions are altered.

[figure not shown]

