#### **4.5 Follow-up**

All trial patients will be ONS flagged for mortality. HRQL data will be collected at 1, 3 and 12 months following treatment for those allocated to an operation. However, for patients randomised to best medical treatment in EVAR Trial 2 we have incorporated a 1 month delay for the early follow-up in these patients. This takes into account the estimated 1 month delay patients will experience waiting for their EVAR procedure in the EVAR arm of trial 2.

Cost evaluation will be based on operation costs and in patient admissions during the course of follow up. The incidence of any adverse events will also be collected at every follow-up appointment, eg. tender AAA, ruptured AAA, conversion to open repair, myocardial infarction, stroke, renal failure and amputation. CT scan will be used for assessment of growth rates, persistent endoleaks and durability which could vary with stent graft type. CT scan follow-up will be at 1 and 3 months, 1 year, 2 years, 3 years and 4 years for EVAR patients in trial 1 or 2. CT scan follow up will be performed annually for patients randomised to EVAR Trial 1 OR. CT scan follow up will be annually for best medical treatment patients in EVAR Trial 2. Creatinine will be recorded annually for all patients to assess any changes in renal function between the randomised groups.

[figure not shown]
Figure 8 illustrates the treatment procedure for each patient.

*Figure 8 – Patient treatment procedure within EVAR Trials*

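### Trial 2 quality-of-life questionnaires have two different control schedules, a 12-month comparison about one month out of step, and no due date for EVAR patients who are not operated on

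*Protocol*

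**What the plan says.** Section 4.3 sets a questionnaire at recruitment and then at "one, three and 12 months after surgery or the beginning of medical treatment as appropriate". The sentence covers both trials and gives the medical-treatment arm no delay.

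Section 4.5 repeats the schedule for the surgical arms: "HRQL data will be collected at 1, 3 and 12 months following treatment for those allocated to an operation". It then makes an exception for Trial 2 patients randomised to best medical treatment: "we have incorporated a 1 month delay for the early follow-up in these patients". The reason given is "the estimated 1 month delay patients will experience waiting for their EVAR procedure in the EVAR arm of trial 2". Section 4.5 does not say which visits are early, and it does not mention moving the 12-month visit.

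Neither section gives a date for a patient allocated to surgery who does not have it. Section 3.5(e), on Trial 2, says of best medical treatment: "Best medical treatment will be offered to the whole group". Its start is therefore an event that both arms share, but the EVAR arm is not timed from it.

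The EuroQol is one of the questionnaires. Section 4.4 says that "cost per quality-adjusted life year (QALY) can be constructed from changes in mortality (if any) and in HRQL".

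**The concern.** A randomised comparison of quality of life should assess both arms at the same time since randomisation and give every surviving patient the same chance of being assessed. Here the EVAR clock starts at an operation that follows a wait, while the control clock starts with medical treatment. The one-month delay in section 4.5 shows that the authors saw this, but section 4.3 omits it and section 4.5 leaves its extent open. A co-ordinator cannot follow both sections.

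A clock that starts at operation also never starts for someone who refuses, deteriorates or keeps waiting. The control arm has no such filter. If those patients receive no questionnaire, the EVAR arm is reduced to operated patients, a group defined after randomisation. Quality of life is a stated outcome of both trials, and EuroQol scores may feed the cost per QALY.

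**Working it through.** The protocol gives no effect size, standard deviation or power for quality of life, so there is no planned figure to reproduce. The check is visit-time arithmetic, in months from randomisation.

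**Inputs**
- Nominal visits v = 1, 3, 12 (sections 4.3 and 4.5).
- Wait for EVAR w = 1, an estimate with no spread or maximum given (section 4.5).
- Control delay d at each visit: 0 under section 4.3; 1 at the early visits under section 4.5.
- Assumption: controls start medical treatment at randomisation.

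**Formulae**
- EVAR visit = w + v
- Control visit = v + d
- Gap (EVAR minus control) = w − d

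A visit is aligned only where the delay equals the wait.

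**At the protocol's own wait, w = 1.** EVAR visits fall at 1+1, 1+3 and 1+12, that is 2, 4 and 13 months.

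| Rule for controls | Control visits | Gaps (months) |
|---|---|---|
| Section 4.3, no delay | 1, 3, 12 | 1, 1, 1 |
| Section 4.5, only the first visit early | 2, 3, 12 | 0, 1, 1 |
| Section 4.5, first two visits early | 2, 4, 12 | 0, 0, 1 |
| Section 4.5, all three visits delayed | 2, 4, 13 | 0, 0, 0 |

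The third row is the most natural reading, since early, coming straight after a list ending at 12 months, would not ordinarily include month 12. Only the last row removes every gap, and neither section states it.

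**At other waits (assumed range 0.5 to 3 months)**

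| Wait | Section 4.3 gaps | Section 4.5, first two early | Section 4.5, all delayed |
|---|---|---|---|
| 0.5 | 0.5, 0.5, 0.5 | −0.5, −0.5, 0.5 | −0.5, −0.5, −0.5 |
| 2 | 2, 2, 2 | 1, 1, 2 | 1, 1, 1 |
| 3 | 3, 3, 3 | 2, 2, 3 | 2, 2, 2 |

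At these waits no reading aligns all three visits, because a fixed delay matches only a wait of the same length.

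**Patients not operated on.** With no operation there is no w, so w + v is undefined and no visit falls due. The documents do not say how many such patients to expect.

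**With fixed times from randomisation**, the gap is 0 at every visit whatever the wait, and every surviving patient has a due date. The interval from operation to questionnaire becomes (2, 4, 13) − w: 1, 3, 12 if w = 1; 0, 2, 11 if w = 2; −1, 1, 10 if w = 3.

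**The case against.** The strongest defence is that section 4.3 states a general rule for both trials and section 4.5 a deliberate, reasoned exception for Trial 2 controls. Read that way the authors aligned the early visits, where recovery from surgery makes timing matter most, and what is left is one month in 13. This largely stands. It reduces the problem but does not remove it: section 4.3 is unqualified for controls, early is undefined, and the last visit stays offset on the natural reading.

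It can also be said that unoperated EVAR patients could be dated from the start of medical treatment, since the whole Trial 2 group is offered it, and that nothing excludes them. That is possible under section 4.3, but section 4.5 times patients allocated to surgery from their treatment and offers no fallback. The text contains a gap, not a stated exclusion. Figure 8 is not shown and may contain a schedule; nothing is inferred from its absence, and it would not remove the difference between the two sections.

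Stronger readings are tempting in three places, and the documents do not support them.
- *Deaths during the wait select the EVAR arm.* A reader might convert the 25% annual control mortality in section 4.1 into a monthly loss from the EVAR arm. Before any operation, comparable controls would be expected to die at the same rate, and they return no later questionnaire either. Deaths are also captured by ONS flagging. The selection question concerns living, unoperated patients.
- *The cost-utility result is biased.* Section 4.4 undertakes that analysis only if one treatment is clinically better at higher cost, and QALYs can use actual completion dates. Those dates cannot replace questionnaires that were never due, but no bias in the result is demonstrated.
- *Trial 1 is misaligned too.* Both its arms are timed from surgery, and the documents show no difference in waits.

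**Conclusion.** The point holds for Trial 2. The two sections give different control schedules. On the protocol's own one-month wait, and assuming controls start medical treatment at randomisation, the 12-month comparison is offset by about one month under section 4.3 and under the natural reading of section 4.5. Waits other than one month also offset the visits that the delay was meant to align. Surviving patients allocated to EVAR but not operated on have no stated due date, so quality-of-life and EuroQol data in that arm risk coming only from operated patients.

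The resulting bias cannot be sized from the documents, which give neither the distribution of waits, nor the number of unoperated patients, nor the change in quality of life between months 12 and 13. It is probably modest. The correction is still worth making because the protocol itself fixes the visit times, and an analysis plan cannot recover questionnaires that were never sent. In Trial 1 the only gap is the missing due date for unoperated patients.

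**What to change.** Reconcile sections 4.3 and 4.5 by stating one Trial 2 questionnaire schedule, counted from randomisation in both arms. Baseline, 2, 4 and 13 months would serve: it extends the existing one-month delay to the last visit and keeps the intended post-operative spacing when the wait is one month. State that the questionnaire goes to every surviving randomised patient, whether or not the operation has taken place. In Trial 1 keep the present time origin and add a due date for patients who are not operated on. How deaths are scored and which patients are analysed can be left to the analysis plan.

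The cost is wording in two sections and the co-ordinators' mailing dates. The drawback is that the interval from operation to questionnaire will vary when the wait is not one month, and after a long wait an early questionnaire may precede surgery. Recording the operation and completion dates would let the analysis describe that variation.

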#### 4.4 Economic Evaluation

Within each of the two sub-trials the type and extent of economic evaluation will depend crucially upon the clinical outcome of that trial:

1. If one technology produces a clinically better outcome than another at significantly lower cost, then clinical and financial criteria both lead to the same conclusion.
2. If there is no clinically significant difference in outcome between two technologies under comparison, then the least cost option is preferable (cost minimisation analysis).
3. If one technology produces a clinically better outcome than another at higher cost, then we shall undertake marginal cost-utility analysis (based on mortality and the EuroQol) and, if appropriate, marginal cost-effectiveness analysis (based on the Patient Generated Index (PGI)).

NHS costs will be collected. These will include the length of time in hospital (subdivided into intensive care, high dependency care, acute care and convalescent care), and theatre costs (subdivided into the length of operation and the use of staff, tests and drugs).

Under scenario 3 we shall use the EuroQol to estimate changes in health utility. One advantage of using the EuroQol is that it expresses changes in HRQL on a ratio scale. Thus cost-utility ratios in the form of cost per quality-adjusted life year (QALY) can be constructed from changes in mortality (if any) and in HRQL. Comparisons can then be made with other health care interventions. If there is no significant change in mortality, however, care will be needed because the EuroQol is less responsive to change than most condition-specific measures. To reduce the possibility of a Type II error, we shall also undertake a cost-effectiveness analysis based on the PGI.

We shall subject our results to extensive sensitivity analysis. First we shall identify the critical components of the cost and outcome by varying all estimated parameters in the analysis individually, to see how the economic findings are affected. Those parameters which lead to substantial changes in these findings will be varied over plausible ranges in combination to see whether the main conclusions are altered.

[figure not shown]
As this economic evaluation is being undertaken alongside a randomised trial, both cost and outcome data will be subject to random variation. Therefore we shall estimate confidence intervals for costs, outcomes, cost-utility ratios and cost-effectiveness ratios. The last two will use the resampling technique known as bootstrapping.

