### **3.7 Financial provision for complete data collection**

It is essential that high quality data is collected for all patients randomised in the EVAR Trials. To encourage good data retrieval, trial co-ordinators based at each of the 13 participating centres will be paid an additional amount of money on receipt of clean and complete data at Charing Cross. An estimate has been made of the length of time a trial co-ordinator will take to complete the case report forms, (1 hour for a baseline assessment and 20 minutes for a follow up appointment). A £25 payment will be made for each complete baseline assessment and a further £25 payment for the operation data. A £25 payment will also be made on receipt of each complete set of follow-up data.

Treatment costs	EVAR	OR
Theatre, surgeon, anaesthetist, nurse, sutures, current device *	3.7 hours = £924	3.7 hours = £924
AAA repair device **	£5,000	0
Wires, catheters for radiologists **	£800	0
Consultant radiologist *** (2 day)	£378	0
Senior radiographer grade I *** (2 day)	£146	0
Radiology nurse, Grade F *** (2 day)	£141	0
Post operative CT scans (£250 each) at 1/12, 3/12, 6/12, 1, 2, 3, 4 years	£1,750	£1,750
Totals	£9,139	£2,674

Net treatment cost for EVAR 2 = £9,139  
(70 randomised per year => 35 for EVAR)

Net treatment cost for EVAR 1 = EVAR - OR  
= 9,139 - 2,674 = £6,465  
(200 randomised per year => 100 for EVAR)

\* taken from "Resource use and costs of elective surgery for asymptomatic abdominal aortic aneurysm" R.G. Jepson, J.F. Forbes, F.G.R. Fowkes  
European Journal of Vascular and Endovascular Surgery, 1997, Vol 14.

\*\* Manufacturers price lists

\*\*\* NHS salary scales 1998

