**Figure 5 -Treatment costs of EVAR (EVAR Trial 2) and net costs over OR (EVAR Trial 1)**

Service costs	EVAR	OR
Pre operative duplex and CT scans *	£513	£513
Pre operative assessment days ** (standard rate, £112 per day) *	2 days = £224	1 day = £112
Post operative ITU days ** (standard rate, £797 per day) *	0	1 day = £797
Post operative HDU days ** (standard rate, £398 per day) *	7 days = £2,786	0
Post operative standard days ** (standard rate, £112 per day) *	0	9 days = £1,008
Totals	£3,523	£2,430

Net service cost for EVAR 2 = £3,523

Net service cost for EVAR 1 = EVAR - OR  
= 3,523 - 2,430 = £1,093

\* taken from “Resource use and costs of elective surgery for asymptomatic abdominal aortic aneurysm” *R.G. Jepson, J.F. Forbes, F.G.R. Fowkes* European Journal of Vascular and Endovascular Surgery, 1997, Vol 14.

\*\* taken from “UK Small Aneurysm Trial” papers  
Lancet 21st November 1998

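### A bootstrap confidence interval on the cost-per-QALY ratio can become unreadable when the QALY difference is close to zero, even in cases where the same data settle whether EVAR is worth its extra cost

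*Protocol*

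**What the plan says.** Protocol section 4.4 sets out three cases.

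- **Scenario 1:** "If one technology produces a clinically better outcome than another at significantly lower cost", the clinical and financial criteria agree and no ratio is needed.
- **Scenario 2:** "If there is no clinically significant difference in outcome between two technologies under comparison, then the least cost option is preferable", that is, cost minimisation, again without a ratio.
- **Scenario 3:** "If one technology produces a clinically better outcome than another at higher cost, then we shall undertake marginal cost-utility analysis", with a cost-effectiveness analysis on the Patient Generated Index (PGI) where appropriate.

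Under scenario 3, "cost-utility ratios in the form of cost per quality-adjusted life year (QALY) can be constructed from changes in mortality (if any) and in HRQL". The section also considers this analysis when mortality does not change significantly, and warns that the EuroQol is then relatively unresponsive.

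On uncertainty it says: "Therefore we shall estimate confidence intervals for costs, outcomes, cost-utility ratios and cost-effectiveness ratios". It adds: "The last two will use the resampling technique known as bootstrapping". The bootstrap variant is not named. Nothing is said about replicates whose effect difference is zero or negative, and neither net benefit nor the cost-effectiveness plane is mentioned.

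**The concern.** Cost-effectiveness is the commissioning question quoted in section 2.1. The measure of uncertainty chosen for it is an interval on cost difference divided by QALY difference.

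That quantity is discontinuous where the QALY difference is zero. Suppose EVAR costs more. Replicates with a tiny gain give huge positive ratios, and replicates with a tiny loss give huge negative ones. Ranked from low to high, the dearer-and-worse replicates fall at the low end, which looks favourable. Once they exceed about 2.5% of the total, the lower percentile limit becomes negative. The interval then covers every plausible willingness-to-pay value. It tells the reader that the QALY difference could be zero, but not whether EVAR is worth its cost.

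Scenario 3 is entered on a clinical judgement, not on the precision of the QALY difference, so it does not exclude this situation. The PGI ratio has the same weakness in its denominator.

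**Working it through.** **Protocol inputs**

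- Trial 1 net treatment cost (section 3.7, Figure 5): "9,139 - 2,674 = £6,465". Net service cost (Figure 6): "3,523 - 2,430 = £1,093". Both subtractions are correct. Total: 6,465 + 1,093 = £7,558.
- Trial 2 total: 9,139 + 3,523 = £12,662.
- Patients (Summary): 800 and 300, so about 400 and 150 per arm.
- 30-day mortality (section 4.1, Figure 7): 11/191 = 5.76% for open repair and 2/180 = 1.1% for EVAR, a difference of 4.65 points. These rates reproduce the protocol's 361 per arm (two-sided 5%, 90% power, continuity correction).

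The protocol gives no figure for the ratio or its interval, so there is none to reproduce.

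**Assumptions not in the documents:** 12-month horizon; utility 0.75; QALY SD 0.15-0.40 in Trial 1 and 0.20-0.40 in Trial 2; cost SD £6,000 (Trial 1) and £8,000 (Trial 2); cost and QALY independent; £30,000 per QALY; percentile limits.

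**Step 1: when the interval breaks.** SE of the QALY difference = SD × √(2/n). The share of replicates below zero is Φ(−z), where z = gain/SE. It passes 2.5% when z falls below 1.96.

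**Step 2: Trial 1 at the planning mortality.** Gain = 0.0465 × 0.75 × 1 year ≈ 0.035. Ratio ≈ £217,000 per QALY.

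| QALY SD | z | Replicates below 0 | 95% ratio interval |
|---|---|---|---|
| 0.20 | 2.47 | 0.7% | £116,000 to £870,000 |
| 0.25 | 1.97 | 2.4% | £83,000 to £1.35m |
| 0.30 | 1.64 | 5.0% | −£1.14m to £1.70m |
| 0.40 | 1.23 | 10.8% | −£1.80m to £2.12m |

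**Step 3: the same data as net benefit.** Net benefit = 30,000 × QALY difference − cost difference.

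Trial 1, gain 0.020, SD 0.25:
- Estimate: 600 − 7,558 = −£6,958.
- SE: √[(30,000 × 0.0177)² + (6,000 × √(2/400))²] ≈ £679.
- 95% interval: about −£8,290 to −£5,630, clearly negative.
- Ratio interval: about −£3.3m to £3.9m.

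Trial 2, 150 per arm, gain 0.050, SD 0.30:
- Estimate: 1,500 − 12,662 = −£11,162.
- 95% interval: about −£13,890 to −£8,440.
- Ratio interval: −£1.77m to £2.28m.

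**Step 4: does scenario 3 prevent this?** Simulated Trial 1 trials at 5.76% v 1.1% were kept only if 30-day mortality was significantly lower with EVAR (about 97% of them). This used survivor QALY SD 0.15-0.30, cost SD £5,000 and 0-5% later deaths. Among the trials kept, the lower ratio limit was negative in roughly 30-40% at SD 0.15, rising to about 70% at SD 0.30. The net-benefit interval excluded zero in about 100%.

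**Step 5: longer horizon.** Assume four years, gain 0.115, QALY SD 1.0 and cost SD £8,000. The ratio interval excludes £20,000 in 27% of trials against 94% for net benefit. At £30,000 the figures are 0% and 48%. Net benefit still does better, but it is no longer decisive in nearly every trial.

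**The case against.** **The scenarios limit the damage.** A reader might infer that a dominated EVAR would be reported as merely uncertain. Section 4.4 does not support that: a technology that is better and cheaper falls under scenario 1 and clinically equal outcomes under scenario 2, and neither leads to a ratio. A dominated QALY result could reach a ratio only if EVAR were judged clinically better while its QALY estimate was at or below zero. The scenarios also reduce how often the problem arises. At 5.76% v 3.2% mortality with SD 0.25, and again reading clinically better as a significant 30-day mortality difference, only 42% of simulated trials reach a ratio. Of all trials, 27% reach one and fail to exclude £30,000. At 5.76% v 1.1% the filter hardly helps: 47% still fail.

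**Other planned intervals keep much of the evidence.** A reader might also infer that the trial would throw its evidence away. It would not, because separate intervals for costs and outcomes are planned. With gain 0.018, SD 0.25 and cost SD £5,000, the upper QALY limit is 0.018 + 1.96 × 0.0177 ≈ 0.053. The lower cost limit is 7,558 − 1.96 × 354 ≈ £6,865. Together they imply more than about £130,000 per QALY for any gain within the limits. This stands, although readers must then make the joint inference themselves.

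**Detail may belong in an analysis plan.** The bootstrap variant and the graphical display often do. But the protocol itself fixes the ratio as the quantity to receive the interval, and that is the choice at issue.

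**The sizes rest on outside inputs.** This is correct. The protocol gives no SDs, threshold or QALY horizon, and £7,558 is a pre-trial estimate.

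**Conclusion.** The point holds in limited form. The planned interval on the ratio can be uninterpretable under scenario 3 while the same data answer the value-for-money question. On the protocol's own costs, sample size and planning mortality, and under the stated 12-month assumptions, this would affect about 30-70% of Trial 1 trials that show a significant mortality benefit. The range follows the assumed survivor QALY SD.

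The interval does not always fail. It is readable when the QALY z-value is above about 1.96, and at the planning effect with SD 0.25 it lies wholly above the assumed threshold. The advantage of net benefit narrows over a longer horizon. Clear dominance and clinically equal outcomes are outside this point. It is a worthwhile, inexpensive improvement to the analysis and does not undermine the trial's design.

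**What to change.** In the closing paragraph of section 4.4:

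- Keep the cost-utility and cost-effectiveness ratios as point estimates.
- Bootstrap patients within arm, keeping each patient's cost and QALY together.
- Show the replicates on the cost-effectiveness plane.
- Report the 95% interval for incremental net benefit (or the probability that EVAR is cost-effective) over a stated range of willingness-to-pay values.
- Give an interval for a ratio, including the PGI ratio, only when essentially all replicates (for example over 99%) have an effect difference of the same sign.

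This costs one paragraph of wording. It uses the same data and replicates, with no extra patients or procedures. The small downside is that a range of willingness-to-pay values must be stated.
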